1.0 Objectives

1.1 Purpose:

This study will provide preliminary data to demonstrate feasibility and acceptability of time-restricted eating (TRE) in the family unit, providing critical preliminary data to support NIH-level funding for a more detailed analysis of TRE in families.

Obesity affects over 40% of adults and over 25% of children in the United States. Obesity – defined in adults as a body mass index (BMI) $\geq 30 \text{ kg/m}^2$ and in children as BMI $\geq 95^{\text{th}}$ percentile – is associated with several physical and psychological comorbidities, such as hypertension, heart disease, type 2 diabetes mellitus, and reduced quality of life. Heritability of obesity is 40-75%. Thus, if a parent is obese, children in the family have a high likelihood of also becoming obese due to both genetic and environmental factors. As such, treatments that apply to the family unit can address the public health concern of obesity at the child and adult level.

Typically, obesity treatment primarily focuses on intentional caloric restriction. In adults with obesity, behavior-based weight loss programs result in weight reduction of 1-4 kg over one year. In children with obesity, lifestyle modification therapy typically results in weight stabilization, while children without treatment gain weight. Weight stabilization results in reductions in body mass index parameters (e.g., percent BMI or BMI z-score) due to increased height in children. Family-based obesity treatment also focuses on intentional caloric restriction through reduced consumption of energy dense foods, as well as increased consumption of low energy density foods, increased physical activity, and implementation of strategic parenting practices. Parent BMI change is a significant predictor of child outcomes in family-based treatment. Unfortunately, family-based interventions are typically time and resource intensive, thus limiting their receptiveness by many families.

In contrast to intentionally restricting calories, time-restricted eating (TRE) intentionally restricts the eating window while allowing ad libitum intake during the window. TRE's agnostic approach to eating allows individuals to select foods that align with their needs and preferences. Multiple studies in adults, including our own, demonstrate TRE reduces weight. The postulated mechanism is that a reduced eating window reduces the number of eating occasions to reduce daily caloric intake.

2.0 Background

2.1 Significance of Research Question/Purpose:

Rigorous prior research in small-scale human studies show promising effects of TRE. In contrast to intentional caloric restriction, TRE presents a simplified

MEDICAL PROTOCOL (HRP-590)

PROTOCOL TITLE: Piloting a Family-Based Intervention of Time-Restricted Eating to Treat Obesity

VERSION DATE: 07Sep2022

approach to obesity treatment. TRE establishes a consistent daily eating window (~8-12 hours) with *ad libitum* intake, while preserving a daily 12-16 hour fasting period. Our preliminary data in adults (PI: [name]), show that 12 weeks of TRE with *ad libitum* intake in adults who are overweight results in reduction of weight (-3.7%), fat mass (-4%) and visceral fat (-11.1%).¹ Moreover, our preliminary data show that TRE improves quality of life relative to baseline or unrestricted eating.²

TRE's agnostic approach to diet allows participants to eat *ad libitum* during their eating window according to food availability and cultural food preferences. Consequently, TRE presents a practical means of implementing prolonged fasting in adults, reducing eating occasions by 22%¹ and daily caloric intake by ~8-20%.^{3,4} TRE can be administered remotely, reducing frequently cited barriers to intentional caloric restriction such as transportation, scheduling or financial barriers.^{5,6} TRE requires less staff time, as our preliminary data show that the average visit duration for monitoring intentional caloric restriction in adults was 46.1 (33.7) [mean (SD)] minutes, whereas the duration for TRE was significantly lower ($p<0.01$) at 24.4 (7.7) minutes.² In summary, TRE's simple approach of restricting the eating window results in weight reduction and increased quality of life while taking less staff and participant time than traditional obesity treatment approaches, likely increasing acceptability of TRE.

It is well documented that obesity clusters in families. As such, obesity treatment should be made available to both children and adults, simultaneously.

Traditionally, family-based therapy has been implemented by a few research groups and is time and resource intensive.^{7,8} Even on an individual level, multiple barriers likely impede the implementation and effectiveness of, as well as adherence to intentional caloric restriction. In contrast, TRE's simple approach presents a potentially viable alternative to intentional caloric restriction. By allowing *ad libitum* intake during the eating window, TRE mitigates the understanding, literacy, dietary, and numeracy barriers often arising from intentional caloric restriction.⁵ Furthermore, the contact hours necessary to implement TRE will be significantly less than other interventions. This study will provide preliminary data to demonstrate feasibility and acceptability of TRE in the family unit, providing critical preliminary data to support NIH-level funding for a more detailed analysis of TRE in families.

3.0 Study Endpoints/Events/Outcomes

- 3.1 Primary Endpoint/Event/Outcome: Evaluate feasibility and acceptability of implementing TRE in families by quantifying recruitment, adherence and intervention burden. We anticipate that we will recruit ~3 families per month for a total of 10 families in each intervention group (N=20), with a retention rate of 70-80% across both groups.

MEDICAL PROTOCOL (HRP-590)

PROTOCOL TITLE: Piloting a Family-Based Intervention of Time-Restricted Eating to Treat Obesity

VERSION DATE: 07Sep2022

- In the TRE group, there will be close agreement between tooth brushing times (recorded with Bluetooth-enabled toothbrush) and self-reported eating window.
- Family-based TRE will result in less intervention burden than intentional caloric restriction, as documented by less staff time administering the intervention.

[figure not shown]
3.2 Secondary Endpoint(s)/Event(s)/Outcome(s):

- Compare weight/BMI change between the TRE group and the SOC group. We hypothesize that the weight/BMI outcomes between the two groups will be comparable.
- Assess relationship between child and adult weight/BMI outcomes with TRE. We hypothesize that parent and child weight/BMI change will be positively correlated.

4.0 Study Intervention(s)/Investigational Agent(s)

4.1 Description:

This pilot study will be designed as a 12-week randomized trial comparing the effects of family-based TRE to family-based intentional caloric restriction (standard of care) on weight (Figure 1). Our study is innovative in using mobile technology to monitor participants and to engage the parent-child dyad in our interventions. We propose the novel concept of providing Bluetooth-enabled electronic toothbrushes to all participants to facilitate monitoring of the eating window. We will also use a Bluetooth-enabled scale for weekly weights by the parent-child dyad to facilitate calculation of the weight trajectory. Finally, we will deliver most sessions virtually by Zoom or by phone.

MEDICAL PROTOCOL (HRP-590)

PROTOCOL TITLE: Piloting a Family-Based Intervention of Time-Restricted Eating to Treat Obesity

VERSION DATE: 07Sep2022

We will enroll 10 family units (i.e., parent/child dyad) per intervention, for an anticipated total of 40 participants and 20 families in the overall study.

Participating families will include children who are 3-9 years old with obesity (BMI $\geq 95^{\text{th}}$ percentile) and a parent with obesity (BMI $\geq 30 \text{ kg/m}^2$).

Consent will be discussed and obtained by a study investigator or the study coordinator via Zoom after explaining the entire study in detail, asking the parent(s)/guardian(s) to explain the purpose, risk and benefits, and other details of the study, and giving them an opportunity to ask questions. A copy of the consent form and assent form will be mailed to the family so that they can review this before the video meeting. At least one parent signature will be required for parental permission. However, the study team will encourage both parents/guardians to be present at the initial visit to learn about the study and ask questions. We will ask that the parents return the signed/dated consent form and assent form for counter signature by the individual who conducted the video consent process. As children under the age of 8 will be enrolled, we will take a verbal consent as an agreement to participate and will not enroll the child if the child gives verbal dissent.

In the TRE group, study staff will instruct the family unit on limiting the eating window to 10-12 hours per day, during which they can eat ad libitum. Notably, in the TRE group, participants (children and adults) will be instructed to brush their teeth with a Bluetooth-enabled toothbrush in the morning and specifically within $\frac{1}{2}$ hour after their evening meal. This will serve as a cue to stop evening eating, and information from the Bluetooth-enabled toothbrush will be accessed by study staff to approximate the eating window. The adult from each family unit will receive a periodic REDCap-administered emails to indicate the timing of the first meal of the day and the last meal of the day for the parent and child, which will also serve as an estimate of the eating window.

The standard of care control group will receive dietary instruction that is based on a 1200-1500 calorie diet, as is typical of family-based interventions. Families will be encouraged to follow appropriate portion sizes; increase vegetable, fruit and lean protein consumption; as well as decrease consumption of energy-dense but low-quality items (e.g., sugar sweetened beverages). Families in this group will also receive a Bluetooth-enabled toothbrush and periodic REDCap surveys but will not be instructed on when to brush teeth or to shorten their eating window.

In both intervention groups, the child and adult participant will weigh themselves on a consistently weekly basis, using a Bluetooth-enabled scale. This is a common aspect of behavioral weight loss interventions (i.e., self-monitoring) and will serve as ongoing data collection (see outcomes below). Additionally, treatment will be

MEDICAL PROTOCOL (HRP-590)

PROTOCOL TITLE: Piloting a Family-Based Intervention of Time-Restricted Eating to Treat Obesity

VERSION DATE: 07Sep2022

primarily delivered to the adult participant, as prior research indicates adult-only sessions are as effective as joint sessions for younger children.^{7,9,10} That is, parents and children will attend two in-person sessions: baseline and 12 weeks. Only parents will attend virtual sessions. Sessions occur on a weekly basis for the first 4 weeks and every other week for the final 8 weeks (see Schedule of Events).

4.2 Drug/Device Handling: Not applicable.

4.3 Biosafety: Not applicable.

4.4 Stem Cells: Not applicable.

4.5 Fetal Tissue: Not applicable.

5.0 Procedures Involved

5.1 Study Design: This is a pilot study in which we will explore whether time-restricted eating is acceptable and feasible for a family and whether utilizing TRE is as useful in weight loss as standard of care (calorie control) in families. 20 dyads (a dyad will consist of a parent and a child) will be enrolled. Half of the dyads will be randomized to receive standard of care and the other half of the dyads will be asked to follow a time limited eating program. Here is what will happen for each group:

Standard care: This dyad will be asked to limit calories and will be encouraged to follow appropriate portion sizes, increase their vegetable, fruit and lean protein consumption. Families in this group will also be advised to decrease their consumption of energy-dense but low-quality items such as sugar sweetened beverages. Families in this group will:

- receive Bluetooth-enabled toothbrushes but will not be instructed on when to brush their teeth
- will be asked to fill out periodic REDCap surveys
- will be asked to weigh themselves on a consistent weekly basis utilizing a Bluetooth-enabled scale.
- Treatment will be delivered to the adult participant and the child at baseline and 12-week visits. Parents will be asked to attend Zoom or telephone sessions weekly for the first 4 weeks and every other week for the final 8 weeks of the study.

TRE: This dyad will be asked to limit their eating window to 10-12 hours per day, during which they can eat ad libitum. Families in this group will be asked to:

- brush their teeth twice daily with the Bluetooth-enabled toothbrush: in the morning and then again in the evening within $\frac{1}{2}$ hour of completion of their evening meal. This will serve as a cue to stop evening eating.
- will be asked to fill out periodic REDCap surveys.

MEDICAL PROTOCOL (HRP-590)

PROTOCOL TITLE: Piloting a Family-Based Intervention of Time-Restricted Eating to Treat Obesity

VERSION DATE: 07Sep2022

- will be asked to weigh themselves on a consistent weekly basis utilizing a Bluetooth-enabled scale.
- Treatment will be delivered to the adult participant and the child at baseline and 12-week visits. Parents will be asked to attend Zoom or telephone sessions weekly for the first 4 weeks and every other week for the final 8 weeks of the study.

Schedule of Events

	Prescreening/Consent	Baseline / Week 0	Week 1	Week 2	Week 3	Week 4	Week 5	Week 6	Week 7	Week 8	Week 9	Week 10	Week 11	Week 12	Follow-Up Month 1	Follow-Up Month 3	Follow-Up Month 6
Consent	V																
Dietary treatment session		P	V	V	V	V		V		V		V		P			
Demographics		P															
Height and weight		P												P			
Weight via Bluetooth-scale		X	X	X	X	X	X	X	X	X	X	X	X	X			
Questionnaires																	
• Child Eating Behavior Questionnaire		P/V															
• Adult Eating Behavior Questionnaire																	
• Child Feeding Questionnaire																	
• Peds-QL																	
• Peds-QL Parent Report Versions (aged 2-4, 5-7 or 8-12)															P/V		
• Peds-QL Adult Quality of Life Inventory Questionnaire																	
24-hour recall		V													V		
Satisfaction survey															X	X	X
Daily time log ¹			← to be done via REDCap for 5 consecutive days three times during treatment (e.g., weeks 1, 6 and 12)→														
Use of Bluetooth-toothbrush			← to be done twice daily at home by participants→														

Note: P= in person, V= via virtual visit, X=completion time

¹ All families will receive automated, email-based REDCap survey for the parent to document the time that they and their child started eating in the morning and their last eating occasion of the day. This will serve as a measure of the length of the eating window.

MEDICAL PROTOCOL (HRP-590)

PROTOCOL TITLE: Piloting a Family-Based Intervention of Time-Restricted Eating to Treat Obesity

VERSION DATE: 07Sep2022

5.2 Study Duration:

- It is anticipated that it will take six months to recruit the 20 parent/child dyads (40 individuals total) to participate in the study.
- Each dyad will be enrolled in the study for 12-14 weeks for screening through treatment. Follow up surveys will be sent at 1, 3, and 6 months following the end of treatment.

5.3 Use of radiation: Not applicable.

5.4 Use of Center for Magnetic Resonance Research: Not applicable.

6.0 Data and Specimen Banking: Not applicable.

7.0 Sharing of Results with Participants

7.1 Participants will have access to their scale and toothbrush data results. We will offer to send participants copies of the published data, if they would like to have results of the entire study.

8.0 Study Population

8.1 Inclusion Criteria:

- $BMI \geq 30 \text{ kg/m}^2$ for the parent
- $BMI > 95^{\text{th}}$ percentile for the child
- Age 3-9 years old for the child
- Age ≥ 18 years old for the parent

8.2 Exclusion Criteria

- Concurrent participation in another weight loss study
- Taking any medications for weight loss
- Pregnancy or anticipation of pregnancy in next 6 months (for the parent)
- 3+ on Eating Disorder Survey (see attached)
- Must be on a stable dose of any weight-altering medications

8.3 Prescreening/Consent: Individuals who appear to meet the study criteria based on a pre-screening telephone call will be asked to participate in a virtual (video) visit. At that visit, consent will be discussed and obtained, height and weight will be self-reported by parent for both parent and child, so that estimated BMI can be calculated, and inclusion/exclusion criteria will be reviewed. Individuals who meet the BMI requirement and the inclusion/exclusion criteria will enroll in the study.

Following consent and prior to the Baseline/Week 0 session, parents will be

MEDICAL PROTOCOL (HRP-590)

PROTOCOL TITLE: Piloting a Family-Based Intervention of Time-Restricted Eating to Treat Obesity

VERSION DATE: 07Sep2022

contacted by the University of Minnesota Nutrition Coordinating Center (NCC) staff and will be asked to provide three 24-hour dietary recalls for themselves and for their child (for a total of six). NCC staff will be blinded to participant intervention assignment. Using this 24-hour dietary recall data, we will calculate the daily average caloric intake and healthy eating index, as well as the eating window.

Baseline/Week 0: Individuals will be asked to come to the Delaware Clinical Research Unit (DCRU). At that visit, height and weight will be measured so that BMI can be calculated. Individuals who no longer meet inclusion/exclusion criteria will be excluded (e.g., outside BMI range based on in-person measurement compared to self-reported). Participants who meet the inclusion/exclusion criteria will be randomized to their intervention group. Participants will be provided with a Bluetooth-enabled scale and instructed to weigh themselves once per week. Participants will also be provided with Bluetooth-enabled toothbrushes. Participants randomized to the TRE treatment will be asked to brush their teeth twice daily and to brush their teeth within 30 minutes after the evening meal to note that they have ceased eating until the next day.

Participants randomized to SOC will have a dietary session with a dietitian to discuss food portions and food selections that encourage reduced caloric intake. They will be given portioned dishes as part of this treatment. Participants randomized to TRE will meet with the dietitian to discuss the length and timing of the eating window. All parents will be asked to complete demographic information and questionnaires. Parents will be told that they will receive periodic emails (see schedule of events) asking them to log into REDCap and complete a survey about what time the family started and stopped eating meals for the day.

Weeks 1, Week 2, Week 3, Week 4, Week 6, Week 8, Week 10: Parents will have a dietary session with the dietitian to discuss their respective intervention. That is, parents in TRE will discuss implementation of the eating window and parents in SOC will discuss food portions and food selections that encourage reduced caloric intake. Parents will be reminded that they should utilize the Bluetooth-enabled scale to weigh themselves as well as their child once per week. Parents will be reminded to fill out the REDCap survey daily and will be reminded to utilize the Bluetooth-toothbrush.

Week 12: Participants will return to the Delaware Clinical Research Unit. They will receive a session with the study dietitian. The height and weight of the parent and the child will be measured and BMI calculated. The parent will be asked to fill out questionnaires about eating as well as a satisfaction survey.

MEDICAL PROTOCOL (HRP-590)

PROTOCOL TITLE: Piloting a Family-Based Intervention of Time-Restricted Eating to Treat Obesity

VERSION DATE: 07Sep2022

Parents will be contacted by a Registered Dietician from the University of Minnesota Nutrition Coordinating Center (NCC) staff and will be asked to provide three 24-hour dietary recalls for themselves and for their child (for a total of six).

Follow-up: The parent will receive a satisfaction survey to be completed electronically at 1, 3, and 6 months following treatment .

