15.0 Statistical Considerations

Analysis Plan: We will summarize feasibility and adherence measures (recruitment and retention rate, proportion of days with documented eating window, eating window length) using sample proportions, means (standard deviations), and medians (interquartile ranges). Proportion of families completing the study (retention rate) will be compared between intervention groups using Fisher's exact tests. Agreement between toothbrush reported eating window and survey reported eating window will be evaluated using mixed effects models¹⁶ (to account for repeated measures for each family) and Bland-Altman Plots.¹⁷

The primary outcome analysis will use a linear GEE model, with independence working correlation for family units, to compare change in BMI during the 12-week period (pre-post) between participants assigned to the TRE intervention compared to the standard of care. This model will allow for estimating the TRE effect for children and adults while accounting for the correlation between parent and child measures. If we do not detect a difference in TRE effect for children and adults ($p\text{-value} \geq 0.1$) the treatment assignment by child indicator interaction will be removed from the model. A similar approach will be used to compare changes in measures of diet quality (average caloric intake and HEI), eating and feeding behaviors, appetite, and quality of life measures between groups. Generalized linear mixed effects models will be used to evaluate

MEDICAL PROTOCOL (HRP-590)

PROTOCOL TITLE: Piloting a Family-Based Intervention of Time-Restricted Eating to Treat Obesity

VERSION DATE: 07Sep2022

differences in weight trajectory between intervention groups. We will evaluate the correlation between parent and child change in BMI during the study using Pearson's correlation coefficient, or Spearman's correlation coefficient (if data visualizations indicate a non-linear trend). Total intervention time (sum of session time across the study) will be compared between groups using t-tests (or Wilcoxon rank sum tests if measures are highly skewed).

We will check data distributions before conducting statistical tests and will transform the data if the normality assumption is not met. Logistic regression models will be used in place of linear regression models for binary data, as appropriate. Analyses will be performed in R or SAS (Version 9.4, SAS Institute Inc., Cary, NC)

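### Parent BMI change appears to use two separate height readings, which adds small, avoidable noise (not bias) to an outcome in which only weight can change

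*Combined protocol and SAP*

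**What the plan says.** In Section 8.3, the Baseline/Week 0 paragraph has participants attend the clinical research unit: "At that visit, height and weight will be measured so that BMI can be calculated". The Week 12 paragraph repeats this for both members of the dyad: "The height and weight of the parent and the child will be measured and BMI calculated". The Schedule of Events also lists height and weight at both visits.

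The parent is an adult under Section 8.1: "Age ≥ 18 years old for the parent".

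Section 15.0 uses these measurements twice. A linear GEE with parents and children together is planned "to compare change in BMI during the 12-week period (pre-post) between participants assigned to the TRE intervention compared to the standard of care". Separately, "We will evaluate the correlation between parent and child change in BMI during the study". Section 15.0 also gives the pilot the task of supplying variability estimates for a larger trial.

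No section says which height enters the parent's Week 12 BMI, and none mentions carrying a height forward, averaging heights or taking replicate readings.

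**The concern.** A child aged 3 to 9 can grow in 12 weeks, so a second child height is needed. A parent's true height is fixed over that time, and any difference between the two parent readings is measurement error. BMI divides by height squared, so a relative error in height roughly doubles in BMI.

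Parents supply half of the BMI-change records. The extra error reaches four planned uses:

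- the TRE-SOC contrast;
- the treatment-by-child interaction, which is removed when p ≥ 0.1;
- the parent-child correlation of BMI change;
- the adult SD handed on to the larger trial.

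The question is whether the loss is large enough to matter.

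**Working it through.** **The plan's own figure.** Inputs from Section 15.0: 20 individuals (10 dyads) per group, within-pair correlation ρ from 0.1 to 0.8, alpha 0.05 (taken as two-sided), 80% power. Use an effective n per group of 20/(1+ρ) in a two-sample t-test with 2·n_eff − 2 degrees of freedom.

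- ρ = 0.1: n_eff = 18.18, detectable d = 0.956.
- ρ = 0.8: n_eff = 11.11, detectable d = 1.249.

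The stated 0.96 to 1.25 reproduces. It is in SD units, so height error does not make it wrong. It only raises the kg/m² difference that a given d represents.

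**Assumed inputs (not in the documents).** Parent BMI 36 kg/m², height 165 cm, SD of true 12-week BMI change 1.0 kg/m² for parents and for children, and SD of a single height reading s = 0.3, 0.5 or 0.8 cm.

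**Error added to parent change.** For BMI = W/h², a height error δ shifts BMI by about 2·BMI·δ/h. For 0.5 cm this is 2 × 36 × 0.5/165 = 0.218 kg/m². With two independent readings the error SD of the change is e = (2 × 36/165) × √2 × s. The parent SD becomes √(1 + e²), and the parent-child correlation is multiplied by 1/√(1 + e²).

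| s (cm) | e (kg/m²) | e² | Rise in parent SD | Correlation multiplier |
|---|---|---|---|---|
| 0.3 | 0.185 | 0.034 | 1.7% | 0.98 |
| 0.5 | 0.309 | 0.095 | 4.7% | 0.96 |
| 0.8 | 0.494 | 0.244 | 11.5% | 0.90 |

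**Sensitivity to the true SD, at 0.5 cm.** With SD 0.7 the rise is √(1 + 0.095/0.49) − 1 = 9.3%. With SD 2.0 it is √(1 + 0.095/4) − 1 = 1.2%.

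**Pooled TRE-SOC contrast.** With independence working correlation and one common treatment effect, the contrast is a difference in dyad means. The variance of a dyad mean is proportional to 1 + 1 + 2ρ, that is 2.2 at ρ = 0.1 and 3.6 at ρ = 0.8. Height error adds e² to the parent term only, so the interval widens by √(1 + e²/(2 + 2ρ)) − 1.

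| s (cm) | ρ = 0.1 | ρ = 0.8 |
|---|---|---|
| 0.3 | 0.8% | 0.5% |
| 0.5 | 2.1% | 1.3% |
| 0.8 | 5.4% | 3.3% |

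**Treatment-by-child interaction.** This is a within-dyad contrast with variance proportional to 2 − 2ρ (1.8 or 0.4), so it is more sensitive. At 0.5 cm its standard error rises by √(1 + 0.095/1.8) − 1 = 2.6% at ρ = 0.1 and by √(1 + 0.095/0.4) − 1 = 11% at ρ = 0.8.

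**With one height at both visits.** The height error no longer creates change; it only rescales real change. Section 2.1 cites a 3.7% adult weight reduction, which at BMI 36 is 0.037 × 36 = 1.33 kg/m². A 0.5 cm error alters that by 1.33 × 2 × 0.5/165 = 0.008 kg/m², which is negligible.

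**The case against.** The strongest reply is that this hardly matters. The parent-only figures look larger than the effect on the planned model, which also contains children, and every input to the size is assumed. An SD estimated from 10 parents in one arm has a relative standard error of about 1/√18 = 24%, far above a 5% inflation. If the larger trial derived BMI in the same way, its planning SD ought to include this error. Section 3.2 lists weight/BMI change as secondary (Section 15.0 calls the BMI model the primary outcome analysis), and the weekly scale-weight trajectory gives a comparison that uses no height. All of this stands, and it sets the severity. It does not remove the point, because the noise is avoidable at no cost.

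It is also fair that the plan never says outright that the Week 12 parent BMI uses the Week 12 height. That is the plain reading of Section 8.3, but it is an inference.

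A reader might infer three stronger things that the documents do not support:

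- **That the TRE-SOC difference is biased.** Random error of equal size in both arms leaves it unbiased. The plan describes only the dietary-recall staff as blinded and does not say who measures height, so it gives no evidence of error that differs by arm, though it does not exclude it.
- **That the power statement is wrong.** It reproduces.
- **That the rise in parent variance (3, 10 or 24%) is the loss in the planned comparison.** That figure is a variance and covers parents only. The pooled interval widens far less.

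**Conclusion.** The point holds as a small loss of precision. As written, the plan most plausibly puts two independent height errors into each parent's BMI change. The effect on the pooled comparison is minor when height is measured to about 0.5 cm or better. It grows for the adult-specific estimate, the parent-child correlation and the interaction screen if reading error is larger or within-dyad correlation is high. These sizes rest on the assumed BMI, height, change SDs and reading error. The mechanism does not depend on them; it needs only that adult height is fixed over 12 weeks and that each BMI uses its own visit's height. Severity is low, and the change is optional.

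**What to change.** State in Section 8.3 and Section 15.0 that parent BMI at both Week 0 and Week 12 is computed from the height measured at the baseline clinic visit, and that visit-specific heights are used only for children.

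The baseline height is preferable to the mean of the two parent readings. Averaging would alter the baseline BMI after randomisation, so it could differ from the value used to confirm eligibility. Replicate child readings are not needed for this point.

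The cost is one derivation sentence in each place, with no new data, visit or procedure. Writing it down in advance also removes any choice of height once results are known.
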